8.2 SAFETY AND OTHER ASSESSMENTS

Assessment of hepatic safety: We will follow the current guidance from FDA for assessment of liver safety in those with pre-existing hepatic impairment. Evaluation of Drug Induced Severe Hepatitis (eDISH): eDISH plots will be overlaid from placebo and drug treated arms at the end of the study to look for DILI signals. Those cases with bilirubin > 3x ULN and ALT > 8x ULN will be studied individually and adjudicated for DILI. These data will be provided to the DSMB for concordance with DILI assessment and to IRB and regulatory agencies.

For individual cases, the following rules will be followed for drug discontinuation for DILI:

Since the study population will have evidence of severe liver injury coming in to the trial, these modifications are proposed.

If AST or ALT rise by > 50% from baseline, but are less than 8 times the upper limit of normal and this is associated with less than 3 mg/dl rise in bilirubin, a hepatic panel will be repeated within 24 hours. If the AST and ALT continue to rise or bilirubin rises by 3 mg/dl or more, the study drug will be discontinued.

If AST or ALT exceed 8 times the upper limit of normal at any time or bilirubin rises by 3 or more mg/dl from baseline within a 48-hour time frame, the study drug will be discontinued.

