5 STUDY POPULATION

5.1 INCLUSION CRITERIA

The inclusion and exclusion criteria listed for the CITRIS-AH trial are listed below. The definitions of alcoholic hepatitis and severe sepsis for this study are derived and defined as previously published in the reference literature.

Patients must have a diagnosis from the attending physician or hepatologist of definite or probable alcoholic hepatitis based on NIAAA criteria (2) and suspected or proven infection, and meet 2 out of 4 of the criteria for Systemic Inflammatory Response (SIRS) due to infection or be accompanied by at least 1 criterion for sequential organ failure assessment (SOFA):

1. Alcoholic hepatitis:
 - a. Definite NIAAA alcoholic hepatitis
 - i. Clinical diagnosis and histological confirmation of features of alcoholic hepatitis
 1. Histological diagnosis: liver biopsy with steatohepatitis, lobular inflammation, Mallory-Denk bodies, hepatocyte degeneration or ballooning, “chicken-wire” or portal fibrosis
 2. Clinical diagnosis:
 - a. Chronic alcohol use for at least 5 years (may be intermittent abstinent)
 - b. >1 standard drink per day in women and >2 in men
 - c. AUDIT score >15
 - d. Heavy alcohol use for at least 6 months
 - i. “Heavy use” = average >3 drinks per day (40g) for women and average 4 drinks (50-60g) per day for men
 - e. Onset of jaundice within the past 8 weeks
 - f. Less than 8 weeks of abstinence before onset of jaundice
 - g. Serum bilirubin >3 mg/dL
 - h. AST >50
 - i. AST/ALT ratio >1.5 and levels <400 IU/L
 - b. Probable NIAAA alcoholic hepatitis criteria
 - i. Clinical diagnosis based on heavy alcohol use >5 years
 - ii. Active alcohol use until 4 weeks prior to presentation
 - iii. average >3 drinks per day (40g) for women and average 4 drinks (50-60g) per day for men
 - iv. Sudden onset or worsening of jaundice (bilirubin >3 mg/dL) within past 60 days
 - v. AST/ALT ratio >1.5 and levels <400 IU/L
 - vi. Absence of other causes of liver disease
 1. Negative autoimmune markers (ANA < 1:160, SMA <1:80)
 2. Negative viral hepatitis markers (HAV A IgM, HBV sAg, HBV c IgM, HCV Ab, HCV RNA)
 3. No recent exposure to drugs with DILI potential, as determined by attending physician or hepatologist medication review
 - c. Patients with potential cofounders may be offered transjugular liver biopsy to assess for histological characteristics of alcoholic hepatitis and ruling out other features of chronic liver disease as a part of standard of care

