5.2 EXCLUSION CRITERIA

1. Known allergy to Vitamin C
2. Inability to obtain consent
3. Age < 18 years
4. No indwelling central or peripheral venous or arterial catheter in patients requiring insulin in a manner that requires glucose being checked more than twice daily (e.g. continuous infusion, sliding scale)
5. Presence of diabetic ketoacidosis
6. Patient or surrogate or physician not committed to full support (not excluded if patient would receive all supportive care except for cardiac resuscitation);
7. Pregnancy or breast feeding (as documented by urine or serum pregnancy testing)
8. Moribund patient not expected to survive 24 hours
9. Active or history of kidney stone
10. History of chronic kidney disease, stage IIIb or above
11. History of glucose-6-phosphate dehydrogenase (G6PD) deficiency
12. Active malignancy, except non-melanoma skin cancer
13. Uncontrolled upper or lower gastrointestinal bleeding
14. Possible alcoholic hepatitis or other confounding cause of acute hepatitis such as viral, metabolic, autoimmune
15. History of decompensated cirrhosis as indicated by variceal bleeding within 3 months, tense ascites, or hepatocellular carcinoma (HCC)
16. History of liver or other organ transplantation
17. Initial ALT or AST greater than 5 times the upper limit of normal
18. Positive urine or serum toxicology screen and acetaminophen level
19. Non-English speaking
20. Ward of the state (inmate, other)

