10.1.6 SAFETY OVERSIGHT

Safety oversight will be under the direction of a Data and Safety Monitoring Board (DSMB) composed of individuals with the appropriate expertise, including gastroenterology, hepatology, and/or pulmonary critical care. Members of the DSMB should be independent from the study conduct and free of conflict of interest, or measures should be in place to minimize perceived conflict of interest. The DSMB will meet at least every 4 weeks after enrollment of the first subject and until the last enrolled subject completes treatment period to assess safety and efficacy data on each arm of the study. The DSMB will also continue to monitor the study every 4-8 weeks until the last subject completes the 90 day end-of-study time period. The DSMB will operate under the rules of an approved charter that will be written and reviewed at the organizational meeting of the DSMB. At this time, each data element that the DSMB needs to assess will be clearly defined. The DSMB will provide its input to the study team.

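### The eDISH case selection in 8.2 has low sensitivity in this population and can pass over participants whose study drug was stopped for suspected DILI

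*Combined protocol and SAP*

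**What the plan says.** Section 8.2 has two layers.

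- **End-of-study review.** The plan states that "eDISH plots will be overlaid from placebo and drug treated arms at the end of the study to look for DILI signals". Case selection follows: "Those cases with bilirubin > 3x ULN and ALT > 8x ULN will be studied individually and adjudicated for DILI". Both limits are multiples of the ULN, both must be met, and AST plays no part.
- **Individual discontinuation for DILI during treatment.** The section explains that these rules are adapted because participants arrive with severe liver injury. AST or ALT more than 50% above baseline leads to a repeat panel, and to stopping if the rise continues or bilirubin goes up by 3 mg/dL. AST or ALT above 8x ULN, or a bilirubin rise of 3 mg/dL within 48 hours, leads to stopping directly.

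The entry rules fix where participants start. Section 5.1 lists "Serum bilirubin >3 mg/dL" for definite disease and "Sudden onset or worsening of jaundice (bilirubin >3 mg/dL) within past 60 days" for probable disease; both routes also carry "AST/ALT ratio >1.5 and levels <400 IU/L". Section 5.2 excludes "Initial ALT or AST greater than 5 times the upper limit of normal". On oversight, section 10.1.6 says "The DSMB will meet at least every 4 weeks after enrollment of the first subject", with safety and efficacy data reviewed by arm.

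**The concern.** A two-limb screen is useful when each limb carries information. Here the entry criteria largely use up the bilirubin limb, which leaves an ALT limit that is high for a disease whose entry definition places ALT well below AST. The second layer of 8.2 was adapted to liver injury at entry, but the case selection was not. At stake is which cases are individually reviewed for drug injury and then passed to the DSMB, the IRB and regulators. If the selection misses participants who were taken off study drug under the plan's own DILI rules, the adjudicated set is an incomplete account of hepatic safety.

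**Working it through.** The plan derives no figure from these limits, so there is none to reproduce. The documents give no ULNs. I assume bilirubin 1.0 to 1.5 mg/dL, ALT 35 to 55 IU/L and AST 35 to 40 IU/L, and I take values at screening as close to hour 0.

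1. **Bilirubin limb.** The limit is 3 x ULN: 3.0 mg/dL at ULN 1.0, 3.6 at 1.2 and 4.5 at 1.5. Entry is above 3 mg/dL. At ULN 1.0 every participant is over the limit on the entry value. At 1.2 or 1.5, only those entering between 3 and 3.6 or 4.5 mg/dL are not.

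2. **Check against the expected MELD.** Section 9.2 expects a mean of 29. Rearranging the 9.4.2 formula gives ln(bilirubin) = (29 - 6.43 - 9.57 ln Cr - 11.2 ln INR)/3.78. For assumed Cr/INR pairs:
   - 1.5/2.0 gives 18.0 mg/dL
   - 2.0/2.0 gives 8.7
   - 2.0/2.5 gives 4.5
   - 3.0/2.0 gives 3.1
   - 3.0/2.5 gives 1.6, which is below the entry limit

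   High creatinine can therefore produce a MELD of 29 with modest bilirubin. The conclusion rests on the entry floor, not on MELD.

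3. **ALT limb.** ALT at entry is at most 5x ULN, so it must rise at least 8/5 = 1.6-fold. The ratio rule tightens this. With AST at most 5x ULN, AST/ALT above 1.5 and equal ULNs, ALT is below 5/1.5 = 3.3x ULN, and the rise needed is more than 8/3.33 = 2.4-fold. With AST/ALT ULNs of 40/35 the figure is 2.1-fold; with 40/55 it is 3.3-fold. The 400 IU/L cap is looser than 5x ULN at these AST ULNs (5 x 40 = 200).

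4. **Illustration** (ALT ULN 40, starting ALT 60, both assumed). The limit is 8 x 40 = 320 IU/L, a rise of 320/60 = 5.3-fold. A participant going from ALT 60 to 240 and bilirubin 10 to 20 reaches 240/40 = 6x ULN and is not selected.

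5. **Selection set beside the discontinuation rules.** Three routes lead to stopping without selection:
   - The participant in step 4 is stopped if the 10 mg/dL bilirubin rise falls within 48 hours, since 10 exceeds 3.
   - A 3 mg/dL bilirubin rise within 48 hours with ALT unchanged leads to stopping. ALT is still at most 5x ULN.
   - If AST just passes 8x ULN while AST/ALT stays above 1.5 (equal ULNs), ALT is below about 8/1.5 = 5.3x ULN.

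6. **What 10 per arm can show.** With 0 of 10 cases, the one-sided 95% upper bound is 1 - 0.05^(1/10) = 25.9%. At a true risk of 10%, the chance of at least one case on drug is 1 - 0.9^10 = 65%. Fisher's exact test gives p = 0.087 for 4/10 versus 0/10 and p = 0.033 for 5/10 versus 0/10.

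**The case against.** The strongest reply is that the eDISH display is a closing summary and was never the safeguard. The rules that act during treatment are largely relative to baseline, and the participant in the illustration would trigger them. The DSMB sees safety data by arm throughout. All participants appear on the plot whether or not they are selected, and placebo is overlaid, so excess movement on drug can still be seen. Other liver comparisons are planned: liver tests at hours 48, 96 and 168 are secondary endpoints (1.1), changes from baseline are compared by analysis of covariance (9.4.1), and laboratory changes are summarised (9.4.3). The plot axes are not stated, the DSMB charter is not available here, and 8.2 refers to FDA guidance that cannot be consulted here.

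Much of this stands, and it rules out three readings that a reader might infer:

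- **That nearly everyone meets the screen at entry.** The criterion is joint, and section 5.2 keeps initial ALT at or below 5x ULN, so no eligible participant meets it on initial values.
- **That the review cannot separate drug injury from alcoholic hepatitis.** The randomised overlay, the adjudication and the other laboratory analyses give some separation. It is weak mainly because there are 10 per arm, which no change of axis will cure.
- **That an end-of-study plot leaves participants unprotected.** The discontinuation rules and the DSMB meetings operate during treatment.

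None of it answers the narrower point. Being stopped does not put a participant on the adjudication list, and being a point on a plot is not individual review.

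**Conclusion.** The concern holds as one of low sensitivity and internal mismatch. The bilirubin limb adds little, and the ALT limb requires a rise of more than about 2.4-fold from the highest ALT that the entry rules allow (2.1 to 3.3-fold over the assumed ULN pairs), and more from lower starting values. The two layers of 8.2 do not line up: stopping for suspected DILI does not lead to DILI adjudication. That mismatch depends little on the assumed ULNs, because the bilirubin-rise route needs no change in ALT. How many participants would be affected cannot be estimated from the documents. The plan does not time the adjudication separately from the plots, and it does not say whether the DSMB reports include a hepatic display. This is a cheap improvement worth making and does not undermine the trial's safety oversight.

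**What to change.** Make three changes in 8.2:

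- Add an eDISH plot by arm of each participant's peak ALT, peak AST and peak bilirubin as multiples of that participant's hour-0 values. Keep the ULN version as a supplement, and state the ULNs used.
- Select cases for adjudication from the baseline-multiple plot, with cut-offs fixed by the sponsor before unblinding. Also adjudicate every participant whose study drug is stopped under the DILI rules.
- Put the cumulative by-arm plot in the scheduled DSMB reports as well as in the end-of-study analysis.

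The stopping rules themselves are left as they are. The data are already collected: the schedule of activities has bilirubin, AST and ALT at hours 0, 48, 96 and 168. The cost is one recurring figure and a few more cases to adjudicate, some of which will turn out to be natural progression of alcoholic hepatitis.

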8.3 ADVERSE EVENTS AND SERIOUS ADVERSE EVENTS

8.3.1 DEFINITION OF ADVERSE EVENTS (AE)

Adverse event means any untoward medical occurrence associated with the use of an intervention in humans, whether or not considered intervention-related (21 CFR 312.32 (a)).

8.3.2 DEFINITION OF SERIOUS ADVERSE EVENTS (SAE)

An adverse event (AE) or suspected adverse reaction is considered "serious" if, in the view of either the investigator or sponsor, it results in any of the following outcomes: death, a life-threatening adverse event, inpatient hospitalization or prolongation of existing hospitalization, a persistent or significant incapacity or substantial disruption of the ability to conduct normal life functions, or a congenital anomaly/birth defect. Important medical events that may not result in death, be life-threatening, or require hospitalization may be considered serious when, based upon appropriate medical judgment,

they may jeopardize the participant and may require medical or surgical intervention to prevent one of the outcomes listed in this definition.

8.3.3 CLASSIFICATION OF AN ADVERSE EVENT

The following subsections will include a discussion of how AEs will be classified.

8.3.3.1 SEVERITY OF EVENT

All AEs will be assessed by the study clinician using a protocol defined grading system. Describe the method of grading an AE for severity. For example, many toxicity tables are available for use and are adaptable to various study designs. Selection of a toxicity table or severity scale should be made in consultation with the study Medical Monitor.

- **Mild** – Events require minimal or no treatment and do not interfere with the participant’s daily activities.
- **Moderate** – Events result in a low level of inconvenience or concern with the therapeutic measures. Moderate events may cause some interference with functioning.
- **Severe** – Events interrupt a participant’s usual daily activity and may require systemic drug therapy or other treatment. Severe events are usually potentially life-threatening or incapacitating. Of note, the term “severe” does not necessarily equate to “serious”.

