7 STUDY INTERVENTION DISCONTINUATION AND PARTICIPANT DISCONTINUATION/WITHDRAWAL

7.1 DISCONTINUATION OF STUDY INTERVENTION

If subjects do not tolerate the drug due to side effects such as nausea, vomiting, flushing, rash, headache, diarrhea, develops crytalluria on urinalysis, or QTc prolongation >50% baseline, we will reduce the subsequent doses by 50%. If the QTc is greater than 550 msec at any time, the drug will be discontinued.

Loss of indwelling venous/arterial catheter or peripheral intravenous access will also trigger the stopping of Vitamin C infusions but subjects will remain on study. Blood glucose monitoring will continue via the central laboratory for 36 hours after the last infusion via peripheral IV draws or peripheral sticks. Biomarker sampling via peripheral IV and/or peripheral stick is allowable as it occurs only 4 times throughout the study and likely only once (if at all) after the patient has been discharged from the unit and is without a central line.

The study drug will be discontinued if a patient develops a metabolic acidosis unexplained by other etiologies (lactic acidosis secondary to septic shock). Determination of the presence of metabolic acidosis will be made by the clinical care team. Study drug will also be discontinued if primary care team or surrogate decision maker request withdrawal. Data collection will continue on these patients following withdrawal of study drug.

Requests to unblind a patient's study treatment can be made to the study (investigational) pharmacist or clinical care team. Unblinding study treatment should occur only in the case of an emergency when knowledge of the study treatment is essential for subject care to treat a serious adverse event and prevent further harm or death.

If possible, a decision to unblind should be discussed with the Principal Investigator or a sub-Investigator prior to unblinding the study treatment.

If a blind is broken (either intentionally or unintentionally), the circumstances should be documented as to who, what, when, and why and all documentation shall be kept by the study pharmacist.

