9.4.3 SAFETY ANALYSES

Adverse Events

Adverse events will be classified into standard terminology using the Medical Dictionary for Regulatory Activities (MedDRA). Adverse events will be listed by reported verbatim term and MedDRA-preferred term, start and stop date and time, study day, duration, severity, relationship to study drug, and seriousness. Additionally, data may be grouped for analysis by different levels of the MedDRA hierarchy. The incidence of AEs, the incidence of treatment-related AEs, and the severity of AEs will be tabulated by cohort (Vitamin C or placebo). The number and percentage of patients with SAEs and treatment-related SAEs and patients who withdraw due to an AE will be tabulated by cohort (Vitamin C or placebo).

Clinical Laboratory Testing

Clinical laboratory test parameters will be listed for individual patients. Baseline for clinical laboratory parameters will be defined as the last evaluation before the start of the initial dosing with study drug. Summary statistics, including mean absolute change from baseline, will be calculated for each parameter and summarized.

Vital Signs

Vital signs results (systolic and diastolic blood pressure, pulse rate, and body temperature) will be listed for individual patients. Each vital sign measure will be tabulated by evaluation time point. Baseline for vital signs measurements will be defined as the last evaluation before the beginning of the first study drug infusion (Vitamin C or placebo, which will generally be Baseline, pre-dose). Summary statistics, including mean absolute change from baseline, will be determined and tabulated for each measure.

Physical Exams

Physical examination findings at baseline will be listed. Clinically significant changes will be recorded as AEs. Symptoms of interest previously reported with intravenous Vitamin C based on the package insert will be recorded daily, including dizziness, headache, nausea, vomiting, flushing, rash, or diarrhea.

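### The adverse event severity scale is unfinished template text with no laboratory or ECG criteria, so the same inpatient finding can be graded Mild or Severe

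*Combined protocol and SAP*

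**What the plan says.** Section 8.3.3.1 (Severity of Event) opens by saying that the study clinician will grade events with a scale that the protocol defines. Two drafting sentences follow: "Describe the method of grading an AE for severity" and "Selection of a toxicity table or severity scale should be made in consultation with the study Medical Monitor". No table is named there or elsewhere.

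Three grades are then given.

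- **Mild:** "Events require minimal or no treatment and do not interfere with the" participant's daily activities.
- **Moderate:** a low level of inconvenience or concern, with the remark "Moderate events may cause some interference with functioning".
- **Severe:** an event that interrupts the participant's "usual daily activity and may require systemic drug therapy or other treatment", with the remark "Severe events are usually potentially life-threatening or incapacitating".

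Severity is then used in several places. Section 9.4.3 says that "the severity of AEs will be tabulated by cohort (Vitamin C or placebo"). Section 8.3.3.3 makes severity one of three features that decide whether an event is unexpected, and 8.4.1 uses the same three features for unanticipated problems. Section 8.3.5 exempts listed disease-related events, including kidney injury and worsening liver function, from adverse event reporting. An event leaves the exemption if it is linked to the study drug or procedures, or is unexpectedly severe or frequent for that patient. Section 8.3.4 asks for changes in severity to be recorded so that time at each level can be assessed.

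**The concern.** A scale built on daily activity suits outpatients. Section 6.1.2 places every dose on an inpatient unit or in the ICU, section 5.1 admits patients on ventilators or vasopressors or with a low coma score, and section 10.1.1.2 expects most patients to be unable to consent for themselves. Meanwhile the findings that change or stop study drug in 7.1 and 8.2 include QTc, crystalluria, unexplained metabolic acidosis, and rises in AST, ALT or bilirubin. These can occur without any symptom, and the scale has no criterion for them.

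At stake is whether severity means the same thing for each clinician and each patient. If it does not, the by-arm severity table is hard to read. The expectedness judgement and the decision that a disease-related event has become reportable would also rest on an undefined term.

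**Working it through.** The plan gives no figure on this point, so the check is a reading of the definitions against the events that the protocol watches for, followed by one line of arithmetic.

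**Step 1: what each grade requires.** Mild has two joint conditions: little or no treatment, and no interference with activity. Severe has one firm condition, interruption of usual activity. Its treatment clause is permissive (such an event may need treatment), and its danger sentence describes what is usual without stating a criterion. For a patient confined to bed, the firm condition can be read as never met, because there is no usual activity to interrupt, or as always met, because activity is already interrupted.

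**Step 2: apply the grades.**

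| Event | Case for Mild | Case for Severe |
|---|---|---|
| QTc above 550 msec, no symptom. Section 7.1: "If the QTc is greater than 550 msec at any time, the drug will be discontinued" | Both conditions met, assuming no treatment beyond stopping study drug | Danger sentence: potentially life-threatening |
| AST or ALT above 8 times the upper limit of normal, no symptom (8.2 stops study drug) | Both conditions met, same assumption | Danger sentence |
| Brief nausea given a systemic drug, in a patient confined to bed | Treatment may be called minimal; no activity to interfere with | Systemic drug therapy given; activity already interrupted |

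The first two rows show that a marked silent finding can be graded low. The third shows that a minor event can be graded high. In each row two clinicians could follow the text and land at opposite ends. The documents do not say what treatment a QTc above 550 msec would receive, so the Mild reading rests on the assumption shown.

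**Step 3: what else reports these findings.**

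- QTc and crystalluria are safety endpoints at hours 24, 48 and 96 (synopsis). Section 9.4.3 has headings for adverse events, laboratory tests, vital signs and physical examinations, but none for ECG.
- Laboratory values are listed per patient and summarised, including mean change (9.4.3). A mean can hide one extreme value, although the listing would show it.
- eDISH plots overlaid by arm, with case adjudication, cover liver signals only (8.2).
- SAEs are tabulated by arm (9.4.3). For a silent finding that meets no listed outcome, seriousness depends on medical judgement (8.3.2).

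**Step 4: size.** Section 9.2 plans 10 patients per arm. If all 10 enter the safety set and the table counts patients, one patient regraded from Mild to Severe changes that arm's Mild and Severe rows by 1/10 = 10 percentage points each. One patient regraded in each arm, in opposite directions, shifts the between-arm difference by 10 + 10 = 20 points. Section 9.4.3 does not say whether severity is counted by event or by patient.

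**The case against.** The best defence is that the scale does name danger to life, so a clinician facing a QTc above 550 msec can grade it Severe. That stands. A reader might infer that silent events must be graded Mild, but the documents do not support this: the wording permits Mild without forcing it.

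A reader might also infer that the table understates the drug's harms. No direction is shown. Step 2 gives errors both ways, and study drug is blinded with an identical-looking placebo in shrouded bags (6.1.1, 6.2.4), so loose grading should mainly add noise to both arms.

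A third tempting inference is that Hypothesis 1B depends on the severity table. Section 3 defines that objective's endpoint as side effects and serious adverse events. The synopsis lists dose reduction, named symptoms, treatment-related events, QTc and crystalluria. Neither mentions a severity grade.

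The absence of a separate fatal grade is also minor: deaths are captured as SAEs and as mortality to days 28 and 90. Many tolerability items are symptoms, such as headache or nausea, which a communicative ward patient can report. Some events may arise after discharge, since 8.3.4 records them for 7 or 30 days after participation ends, and daily activity is then meaningful. Disease-related events stay in the eCRF even when they are not reportable.

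It may be said that the Medical Monitor will still choose a scale. The text says that one should be chosen, but it also states three definitions that staff would use meanwhile. None of these points supplies a unique grade or an objective criterion.

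**Conclusion.** The point holds as an incomplete and ambiguous definition. For asymptomatic laboratory and ECG findings in ward and ICU patients, 8.3.3.1 gives no unique grade, and the error can run either way. The by-arm severity table may therefore not be interpretable. The expectedness and disease-related-event judgements share the weakness to the extent that they draw on this scale; those sections use the idea of severity without pointing to a grade.

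In size this is a modest, worthwhile correction. Each patient regraded is worth 10 percentage points in an arm of 10, on the assumptions in Step 4. Other safety reporting keeps the important findings visible. The primary endpoint, sample size and power are unaffected. The conclusion rests on the wording of the definitions and the inpatient setting; no misgrading has been shown, and its frequency cannot be estimated from the documents.

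**What to change.** In 8.3.3.1:

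1. Delete the template sentences on describing a method and selecting a table.
2. Replace the three definitions with one named and versioned graded toxicity scale that has numeric laboratory and ECG criteria, for example CTCAE, chosen with the Medical Monitor before enrolment.
3. Add a rule for values already abnormal at hour 0, graded relative to baseline as 9.4.3 defines it. This is needed because entry itself requires bilirubin above 3 mg/dL, so a scale based only on the upper limit of normal would start many patients at a raised grade.
4. Add a short rule for monitored terms that the chosen scale does not cover; check crystalluria in particular.

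In 9.4.3, state that the table shows each patient's maximum grade by arm, and add an ECG display. In 8.3.3.3 and 8.3.5, state whether severity means this grade. The stopping and dose rules in 7.1 and 8.2 are not touched.

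The cost is about a paragraph, a form code list, and the effort of writing the baseline and supplementary rules. Staff must grade against a table as well as by judgement. Five grades will be sparse with 10 patients per arm; pooling adjacent grades for display, with a full listing, would deal with that.
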